3. Client's (qualitative) views on individual therapy sessions assessed with the Helpful Aspects of Therapy form (HAT; Lewlyn, Elliott, Shapiro, Firth, & Hardy, 1988). Completed by therapist in discussion with participant.

Fidelity measure

1. Adherence to ACT related processes assessed with the ACT Fidelity Measure (ACT-FM; O'Neill, Latchford, McCracken & Graham, 2019). Completed by therapist and secondary researcher.

EXPLORATORY OUTCOMES

Adaptations made to treatment will be recorded so that commentary can be made on what adaptations to ACT may be beneficial for older adult clients. **Consideration of the impact that delivering the intervention in a remote manner will also be made and any adaptations that were made to facilitate this.**

TABLE OF OUTCOMES

Objectives	Outcome Measures	Timepoint(s) of evaluation of this outcome measure (if applicable)
Primary Objectives	1. Quality of life (OPQOL-brief).	1. Baselines, pre-, mid- and post-intervention, and at six-week follow up.
Secondary Objectives	Symptom measures 1. Cognitive functioning (MoCA). 2. Changes in levels of anxiety and depression (HADS).	1. At initial contact, by service as standard practice. 2. At initial contact, by service as standard practice. Baselines, pre-, mid- and post-intervention,

		and at six-week follow up.
	Change measures 
 1. Client's goals (PQ). 2. Client's view on change (Change Interview). 	
 1. Prior to each weekly treatment session. 2. One week after finishing treatment.
	Process measure 
 1. Psychological flexibility (CompACT-8). 	
 1. Baselines, pre-, mid- and post-intervention, and at six-week follow up.
	Session measures 
 1. Quality of life/general outcomes (ORS). 2. Therapeutic alliance (SRS). 3. Client's views on the therapy session (HAT). 	
 1-3. At the end of each weekly treatment session.
	Fidelity measures 
 1. Fidelity of treatment (ACT-FM). 	
 1. At the end of each session (by therapist) and random sampling of all sessions (by Secondary Research Supervisor).

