2. Statistical artefacts	Reflect measurement error, outlier to the mean, or experimentwise error.	Assess for reliable change (RCI calculations); stability of client problems through multiple baselines (Pearson/Spearman correlation, visual analysis); replication of change over multiple measures (RCI calculations).
3. Relational artefacts	Superficial artefacts related attempts to please therapist/researcher.	Evaluate client social desirability and determine covariance with measures (ANCOVA); ask ppt their negative and positive descriptions of therapy (Change Interview).
4. Client expectations	Related to expectations or wishful thinking.	Assess client expectations at start; ask ppt whether changes were expected or surprising (Change Interview).
5. Self-correction	Reflect self-help or self-initiated remedy of temporary problems.	Determine direction and stability of measures from baseline to initial sessions (Pearson/Spearman correlation); ask ppt duration of problems using SPQ; look for self-help efforts begun before therapy via demographics form and assessment.
6. Extra-therapy life events	Attributed to life events, e.g., changes in clients' situation.	Monitor for such events; assess likelihood of change without therapy (Change Interview); consider mutual influence these factors have on each other.
7. Psychobiological factors	Attributed to medication, medical illness recovery etc.	Collect information on medication and physical health prior to, and during therapy.
8. Reactive effects	Due to being in research, sense of altruism in client, relationship with researcher.	Ask client directly about effects of research (positive and negative); use of external ratings; minimise research impact.

Note: ANCOVA – Analysis of Covariance; RCI – Reliable Change Index (Jacobson & Truax, 1991); SPQ – Simplified Personal Questionnaire (Elliott, Mack, & Shapiro, 1999); ppt – participant.

STUDY SETTING

The study will be a single centre study, run from a Mental Health Service for Older People (MHSOP) at Lings Bar Hospital, Nottinghamshire.

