At the time of recruitment, all potential participants will be active referrals at the Rushcliffe Mental Health Service for Older People (MHSOP), Lings Bar Hospital, Nottinghamshire. They will also have been referred for further psychology support (i.e. any referral that is felt would benefit from individual clinical psychology sessions). Eligible clients (see inclusion/exclusion criteria) will be informed (through discussion and Participant Information Sheet) about the study during a psychology referral assessment with a Clinical Psychologist from the MHSOP ([name], Field Research Supervisor for the study), delivered by phone/videocall due to social distancing requirements. Adaptations such as larger font on sheets will be determined as well as whether they would be able to facilitate videocall therapy. Potential participants that are interested in taking part will have the CF and PIS posted out to them, with a follow-up call around a week later to obtain consent. Clients that do not consent to take part will be offered usual care from the service.

The Assistant Psychologist from the team will call those participants that consent to determine the dates of the intervention. The Assistant Psychologist will also go through a pack of questionnaires (Questionnaire Pack 1.1 [QP1.1]), which will have been posted out to them. This date will act as Baseline 1. The Assistant Psychologist will then call back a following three times, acting as Baselines 2, 3, and 4, all a week apart. Baseline 4 will ideally be the same day as the start of the Acceptance and Commitment Therapy (ACT) intervention. The ACT intervention will be conducted by the student researcher/therapist via telephone or videocall, depending on the participants wishes. Sessions will be audio recorded using an NHS encrypted electronic device, with participant knowledge, to conduct fidelity checks of the treatment at a later date. Participants will be supported to complete questionnaires after the session which will have been posted out to them.

Therapeutic sessions

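### Baseline stability is assigned to a Pearson/Spearman correlation on four weekly points, which does not measure stability or the size of a drift and can mislead in either direction

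*Combined protocol and SAP*

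**What the plan says.** All references are to the combined protocol and SAP.

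- Data Analysis, Table 2, row 2 (statistical artefacts): "stability of client problems through multiple baselines", to be assessed by "Pearson/Spearman correlation, visual analysis". The row also lists RCI calculations for reliable change and for its replication over measures.
- Table 2, row 5 (self-correction): "Determine direction and stability of measures from baseline to initial sessions". The only statistic named is Pearson/Spearman correlation; visual analysis is not listed. The row adds problem duration from the SPQ and "look for self-help efforts begun before therapy via demographics form and assessment".
- Table 1, row 4 (early change in stable problems) applies correlation and visual analysis to the same baseline-to-early-session window, here as evidence for the affirmative brief.
- Study Regimen, Screening and baseline: after baseline 1, "The Assistant Psychologist will then call back a following three times, acting as Baselines 2, 3, and 4, all a week apart". Also, "Baseline 4 will ideally be the same day as the start of the Acceptance and Commitment Therapy (ACT) intervention".
- Table of Outcomes: OPQOL-brief and CompACT-8 are taken at "Baselines, pre-, mid- and post-intervention, and at six-week follow up". HADS follows the same schedule, plus the service's own score at initial contact. The PQ is taken before each treatment session, and the ORS at the end of each.

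The plan does not say which variables are correlated. It gives no alpha, sidedness or cut-off for calling a baseline stable, and no rule for reading the plots.

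**The concern.** The repeated baselines are the plan's main quantitative guard against two rival explanations of improvement: measurement artefact (including regression to the mean) and problems already resolving before therapy. That guard needs a statistic that shows how far scores moved before session 1, relative to measurement error. A correlation coefficient does not show this, and on four points it is also very imprecise.

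The schedule narrows row 5 further. Its window runs into the first sessions, but OPQOL-brief, HADS and CompACT-8 are not taken in sessions 2-5, and the PQ and ORS have no repeated baselines. No scheduled measure covers both stretches. For the outcome scales, row 5 therefore rests on the same four points as row 2 until the mid-therapy assessment.

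At stake is whether change that began before therapy is recognised as such when the briefs are written. Because Table 1 row 4 uses the same statistic, both briefs can be affected.

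**Working it through.** The plan states no power, alpha or threshold for this check, so there is no figure of its own to reproduce.

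**Inputs.** From the plan: four baselines one week apart, the fourth ideally on the day of session 1 (so the pre-intervention score adds no fifth point); session 12 in week 15; the RCI as the reliable-change criterion. Assumed, because the plan is silent: score correlated with week within a client, two-sided 0.05, linear drift, independent normal errors. Drift is expressed in SEM units because no reliabilities or SDs are given.

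**1. The coefficient does not measure stability.** Invented scores for four weeks:

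| Scores | Movement | Pearson r |
|---|---|---|
| 60, 60.5, 61, 61.5 | 1.5-point drift | 1.00 |
| 40, 55, 35, 45 | 20-point swing | -0.08 |
| 20, 14, 13, 12 | 8-point fall | -0.90 (p = 0.10) |

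The nearly flat series looks least stable and the erratic one most stable. This needs no significance test.

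**2. Thresholds at n = 4.** With no drift, r is uniform on (-1, 1), so two-sided p = 1 - |r|. Significance at 0.05 needs |r| > 0.950, and |r| > 0.5 occurs in 50% of drift-free series. For exact Spearman, 2 of the 24 orderings are perfectly monotone, so the smallest two-sided p is 2/24 = 0.083. Correlating one baseline with another across clients also gives n of at most 4. Lagging the baselines within a client gives n = 3, where |r| must exceed 0.997.

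**3. Power of Pearson.** Weeks 1-4 have a sum of squares of 5. The test is a t-test on 2 df with noncentrality (drift per week in SEM) x sqrt(5).

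| Total drift, baseline 1 to 4 | Pearson flags |
|---|---|
| 1.5 SEM (0.5 per week) | 11% |
| 2.77 SEM (one reliable change, 1.96 x sqrt(2)) | 23% |
| 3 SEM (1 per week) | 26% |
| 4 SEM | 38% |
| 8 SEM | 83% |

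A pre-therapy change as large as the RCI threshold is therefore missed about 77% of the time. With five equally spaced points over the same total drift, the critical |r| is 0.878 and power at 2.77 SEM is 33%. The extra HADS score at initial contact does not rescue that scale: it is outside the weekly series, and inclusion depends on a HADS score of at least 8.

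**4. Alternatives using the SEM.**
- Slope: standard error = SEM/sqrt(5) = 0.447 SEM, so z = slope/(0.447 x SEM). At 0.5 SEM per week the expected z is 1.118 and power 20%. At 1 SEM per week it is 2.236 and power 61%.
- RCI from baseline 1 to baseline 4: z = change/(sqrt(2) x SEM). At 1 SEM per week the expected z is 3/1.414 = 2.121 and power 56%. At 2.77 SEM power is 50%.

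**5. What these depend on.** Both treat the SEM as known. If the true week-to-week SD is k x SEM, the false-alarm rate is 2 x [1 - Phi(1.96/k)]: 12% at k = 1.25 and 19% at k = 1.5.

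**6. Limit of any four-point baseline.** The baselines centre on week 2.5. Projected to week 15, the fitted line has standard error sqrt(1/4 + 12.5^2/5) = 5.61 SEM.

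**The case against.** The strongest reply is that the plan has no statistical gate. It states no alpha and no rule that a non-significant correlation means a stable baseline. Row 2 pairs the correlation with plots, on which a fall of a full reliable change might well be seen. Row 5 asks for direction as well as stability, and the sign of r does give direction; it also uses problem duration and earlier self-help. A sceptic brief is written to argue the non-therapy case, and three clinical psychologists weigh both briefs.

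Much of this stands. A reader might infer that the check almost cannot fail and that pre-therapy improvement will pass as stability. The documents do not support that: it assumes a decision rule they do not contain. If r is instead read descriptively, drift-free baselines will often look as if they are drifting, an error that runs against the therapy. Very large drifts would usually be flagged even by the formal test.

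The reply does not rescue the correlation, which is uninformative about stability on either reading. The plots have no rule, and the analyses are done by the student researcher/therapist. The RCI in row 2 is not assigned to the baseline period, and a pre-to-post RCI cannot separate therapy from drift already under way. The panel judges from briefs built on these analyses.

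A second objection is that the alternatives gain power partly by importing an SEM that the plan does not report, and that the slope test still misses 80% of drifts of 0.5 SEM per week. That is correct. It limits what should be claimed for the change, but it is not a reason to keep a statistic that answers a different question.

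**Conclusion.** The point holds as a matter of analysis choice. The named correlation is unsuitable for judging baseline stability on four points, and no criterion for stability is pre-specified. That leaves row 2 resting on plots without a rule, and row 5 mainly on history. Improvement before session 1 could be read as a stable baseline, or a stable baseline as drifting; the documents do not settle which error is likelier.

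That the coefficient ignores scale is arithmetic and needs no assumption. The power figures rest on the assumptions listed in the working, and would change with a one-sided test (critical |r| 0.900; smallest exact Spearman p 1/24 = 0.042) or with correlated weekly errors. The consequence is limited to one strand of evidence in an adjudicated case record, so this is a worthwhile, cheap improvement and not a fatal flaw.

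**What to change.** 1. In Table 2 rows 2 and 5, and for the baseline part of Table 1 row 4, replace the correlation with drift in SEM units for each client and measure, shown beside the plotted baselines. Use either the four-point slope divided by 0.447 x SEM, or the RCI from baseline 1 to baseline 4, with the same SEM as the pre-to-post RCI. Choose one in advance and state its threshold.
2. Add visual analysis to row 5, so that the plots are examined there too.
3. State the source of each SEM and that it is treated as known, with the false-alarm range of about 12-19% if true weekly SD is 1.25-1.5 SEM.
4. State that finding no drift over three weeks cannot alone rule out self-correction over the therapy period, and must be weighed with the SPQ problem duration and self-help history the plan already collects.

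The cost is wording in three table cells and a spreadsheet formula, with no new data. The downsides are reliance on a published SEM for each scale and a less favourable statement of what the baseline can show.

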Eligibility Criteria	HADS Anxiety or Depression score ≥ 8 ; MoCA score $\geq 22-24$ (criterion dependant on age & education history); active referral to Rushcliffe Mental Health Service for Older People; have capacity to consent to 1:1 therapy; be able to travel to service (alone or with support).
Planned Sample Size	Up to four
Study Duration	Up to 20 months
Objectives	Primary: Efficacy of ACT with older adults experiencing psychological distress. Secondary: Identify change processes of ACT with older adults, with emphasis on the impact of delivering ACT by telephone/videocall (following SARS-CoV-2 social distancing measures).
Outcome Measures	Primary: Quality of life (OPQOL-brief). Secondary: Cognitive functioning (MoCA); levels of anxiety/depression (HADS); Client's goals (PQ); quality of life/general outcomes (ORS); therapeutic alliance (SRS); client's views on the therapy session (HAT); psychological flexibility (CompACT-8); client's view on change (Change Interview); fidelity of treatment (ACT-FM). Exploratory: beneficial adaptations to ACT for older adults. Impact of telephone/videocall therapy on outcomes.
Data Analysis	Reliable Change Index; adjudication panel; Framework Analysis; correlations; visual analysis.

KEY WORDS

Older Adults

Acceptance and Commitment Therapy

Quality of Life

Hermeneutic Single Case Efficacy Design

Change processes

Non-specific factors

Table of Contents

STUDY/TRIAL CONTACTS	3
FUNDER DETAILS	3
STUDY SUMMARY	4
KEY WORDS	4
LIST OF ABBREVIATIONS	7
STUDY MANAGEMENT	8
ROLE OF STUDY SPONSOR AND FUNDER	8
STUDY BACKGROUND and RATIONALE	8
STUDY OBJECTIVES AND PURPOSE	10
PURPOSE	10
PRIMARY OBJECTIVE	10
SECONDARY OBJECTIVE(S)	10
OUTCOME MEASURES	10
PRIMARY OUTCOME MEASURE	10
SECONDARY OUTCOMES	10
EXPLORATORY OUTCOMES	11
TABLE OF OUTCOMES	11
STUDY DESIGN	12
DATA ANALYSIS	13
STUDY SETTING	16
SELECTION OF PARTICIPANTS	16
ELIGIBILITY CRITERIA	16
Inclusion Criteria	16
Exclusion Criteria	16
Sampling and size of sample	17
Sampling technique	17
RECRUITMENT	17
Participant Payment	17
CONSENT	17
STUDY PROCEDURES/REGIMEN	19
STUDY FLOWCHART	19
RANDOMISATION AND BLINDING	20

STUDY REGIMEN	20
SCHEDULE OF PROCEDURES	23
WITHDRAWAL.....	24
ETHICAL AND REGULATORY CONSIDERATIONS.....	24
ASSESSMENT AND MANAGEMENT OF RISK.....	24
ADVERSE EVENTS.....	25
Participant reporting of adverse events.....	26
Participant removal from the study due to adverse events.....	26
ETHICS REVIEW AND COMPLIANCE.....	26
PEER REVIEW.....	27

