To facilitate the cross-referencing of rich case records, several methods of analysis will be employed, dependent on the evidence area required for the affirmative or sceptic brief. These are outlined in Tables 1 and 2, respectively. All analyses will be completed using SPSS (Version 25.0; IBM Corp, 2017) or Microsoft Excel (Version 15.0.5179.1000; Microsoft Corporation, 2013). Analyses will be performed by the student researcher/therapist either at the MHSOP or the Universities of Lincoln or Nottingham. No data containing confidential information will be analysed outside of the MHSOP, in line with relevant NHS Trust policies.

Table 1		
Direct evidence for links between therapy process and outcome, from Elliott (2002).		
Direct evidence area	Description	Method of evaluation (specific analysis method)
1. Retrospective attribution	Change attributed by client to the therapy	Content of Change Interview (Framework Analysis)
2. Process-outcome mapping	Content of post-therapy changes correspond to specific processes within therapy	Correlations between within therapy measures (HAT), and quantitative outcome measures (Pearson correlation, or Spearman correlation if assumptions of normal distribution not met).
3. Within-therapy process-outcome correlation	In-therapy process variables covary with week-to-week changes in client problems	Correlations between ACT adherence and ORS, and the change questionnaire (i.e. the SPQ; Pearson/Spearman correlation)
4. Early change in stable problems	Therapy coincides with changes in long-standing client problems	Change in outcome measures from baseline to initial sessions (Pearson/Spearman correlation, visual analysis)
5. Event-shift sequences	Important events precede stable shifts in client problems, especially if therapy process and client change are logically related	Correspondence between within therapy measure (HAT) and variation in patient's problem (SPQ; Pearson/Spearman correlation, visual analysis)

Note: HAT – Helpful Aspects of Therapy form. SPQ – Simplified Personal Questionnaire.

Table 2

Evidence for links between nontherapy processes and outcome, from Elliott (2002)

Nonchange/ nontherapy area	Changes are...	Method of evaluation (analysis method)
1. Non-improvement	Either trivial or negative.	Assess reliable and clinical significance on measures (RCI calculations); ask ppt the importance and direction of any change (Change Interview).

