2. Not rated higher than Cluster 8 (Mental Health Clustering Booklet 2013/14, Department of Health), a categorisation based on the Health of the Nation Outcome Scale (HoNOS; Wing et al., 1998). Clusters higher than 8 are associated with clients presenting with symptoms of psychosis and it is felt that this level of mental health problem would cause serious heterogeneity between client cases. As standard practice, the MHSOP at Ling Bar Hospital will have rated the client prior to consideration for the study.

3. Inability to understand English to a level required to participate fully in the intervention. This is due to a lack of ability to benefit from the intervention without an interpreter, and the impact an interpreter would have on the non-therapeutic processes (e.g. alliance) being measured in this study.
4. Not currently undertaking any other psychological therapy, talking therapy or counselling. This is due to the potential impact the other therapy could have on change and the inability to fully account for this.

Sampling and size of sample

The study will recruit up to four participants. Most Hermeneutic Single Case Efficacy Designs (HSCED) focus on one client (Stephen, Elliott, & Macleod, 2011). However, there have been recent calls to increase cross case synthesis to further validate the intervention being used (MacLeod, Elliott, & Rodgers, 2012). Three cases would fit with established guidelines for a single-case research series (Smith, 2012) and has shown to be feasible in previous HSCED research (e.g. Wall, Kwee, Hu, & McDonald, 2017). Drop-out or withdrawal would be a major concern with the current study, due to the extended participant contact time and the constraints on recruiting and treating further participants within schedule for Doctoral Thesis submission. With dropout rates around 25% (Grover, Dua, Chakrabarti, & Avasthi, 2018) recruiting up to four participants appears a sensible approach. **A fourth participant will only be recruited up until July 2020, to allow for the completion of the intervention and requirements of submission for the Doctoral Thesis.**

Sampling technique

The sample will be referrals from the MHSOP recruited in a convenience sampling method. As this study aims to reflect usual clinical practice, this is an adequate sampling method to recruit participants.

RECRUITMENT

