psychology referral assessment with potential participants whom have been referred for psychology support, a member of the MHSOP will explain the details of the study and enquire whether they would be interested in taking part. Hard copies of the Consent Form (CF) and Participant Information Sheet (PIS) will be posted out to participants so they able to read through, before a follow-up call is made (around a week later, usually by the same member of the MHSOP) to reiterate a summary of the study and allow an opportunity for any questions relating to the study. Potential participants will then be asked whether they would consent to taking part in the study. Should the potential participant need more time to consider, they will be called back a week later. If potential participants verbally consent, at the time, or after a week, they will be asked whether they consent to each point on the CF in turn. A note of this will be made on the participants clinical notes.

[figure not shown]
Should potential participants not consent to take part in the study, they will be offered usual care from the MHSOP (see STUDY FLOWCHART, below).

The process for obtaining participant informed consent will be in accordance with the REC guidance, and Good Clinical Practice (GCP) and any other regulatory requirements that might be introduced.

Should there be any subsequent amendment to the final protocol, which might affect a participant's participation in the trial, continuing consent will be obtained using an amended CF which will be signed by the participant.

STUDY PROCEDURES/REGIMEN

STUDY FLOWCHART

RANDOMISATION AND BLINDING

Participants in this study will not be randomised or blinded to any aspects of the study. The HSCED methodology allows for a naturalistic and transparent procedural approach to investigating psychotherapy efficacy.

STUDY REGIMEN

Screening and baseline

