Data from throughout the study will be cross-referenced to develop the affirmative and sceptic briefs required for the HSCED. Pseudonyms will be used for the participants and there will be no patient identifiable information within the briefs. Once completed, the briefs will be sent to the expert panel of three Clinical Psychologist, with relevant interest and experience of psychotherapeutic change methods. The panel adjudicate over the case material using a semi-structured questionnaire to decide whether the client made a substantial change and where they attribute this towards (ACT-specific, non-specific, or extra-therapeutic factors). This process allows for a reduction in researcher bias.

SCHEDULE OF PROCEDURES

Procedures	Visits									
	Psychology Screening Assessment & Baseline 1 (wk1)	Baseline 2 (wk2)	Baseline 3 (wk3)	Baseline 4 & Session 1 - pre (wk4)	Sessions 2-5 (wks 5-8)	Session 6 - mid (wk 9)	Sessions 7-11 (wks 10-14)	Session 12 - post (wk 15)	Change Interview (wk 16)	Six wk follow-up (wk 20)
Informed consent	x									
Symptom, & process measures	x	x	x	x		x		x		x
Demographics	x									
Medical history	x						x			
ACT intervention				x	x	x	x	x		
Session, change, & fidelity measures				x	x	x	x	x		
Change Interview									x	

Note: wk = week; see Timetable of Measures for outline of when individual measures are administered.

WITHDRAWAL

Participants may be withdrawn from the trial either at their own request or at the discretion of the Investigator. The participants will be made aware that this will not affect their future care. Participants will be made aware (via the information sheet and consent form) that should they withdraw the data collected to date may not be erased in accordance with the University's Research Privacy Notice and information given in the Participant Information Sheet and may still be used in the final analysis.

Stopping rules and discontinuation:

- If a participant withdraws consent to continue.
- If a participant expresses that the intervention is causing their anxiety and depression to get worse.
- If a participant's physical health significantly deteriorates to a point where continuation would be impractical or create sufficient negative burden on them.
- If a participant fails to comply with the intervention.
- If new findings become published regarding likely risks or negative effects of ACT.

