Should any of these criteria be met, the decision of whether the participant receives further support from the MHSOP will be decided by [name] and the wider MDT at the MHSOP. A replacement participant will be recruited, dependent of timeframe and ability to deliver therapy. Should criteria apply to all participants (such as evidence of the negative effects of ACT), the study as a whole will be temporarily stopped on ethical grounds. Interim analysis would be performed at this point to determine any negative effects of the intervention on the participants. Continuation of the study would be dependent on further guidance from the REC, NHS R&D and any other relevant parties.

ETHICAL AND REGULATORY CONSIDERATIONS

ASSESSMENT AND MANAGEMENT OF RISK

This study aims to reflect usual clinical practice where possible; therefore, the burden to participants will be of a similar level to treatment as usual. That is, they will be expected to attend one-to-one psychotherapy (either face-to-face or at distance) and to discuss their mental health difficulties; what contributed towards the development of their difficulties; and what is maintaining their difficulties. As with any psychological therapy, there is a potential risk that talking about distressing experiences will cause an increase in frequency or intensity of pre-existing mental health conditions.

These risks will be monitored through the study by the Trainee Clinical Psychologist (who is both researcher and therapist) through discussion with the participant, use of outcome measures and importantly by utilising weekly clinical supervision with [name] (Clinical Psychologist for the MHSOP). This allows a space for any concerns to be raised and for [name] to have clinical oversight of the participants. As part of standard clinical practice, and local NHS Trust policies, each participant will have a clinical risk assessment with the MHSOP. This will be reviewed by the researcher/therapist with [name] before starting therapy. Any relevant information will also be added to this, should anything relevant come up in therapy sessions.

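### The ANCOVA on social desirability and the correlations with the HAT form do not fit the data the plan describes

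*Combined protocol and SAP*

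**What the plan says.** **Social desirability.** In Data Analysis, Table 2, row 3 (relational artefacts), the plan gives two methods. One is "Evaluate client social desirability and determine covariance with measures", with ANCOVA as the technique. The other is to ask about good and bad aspects of therapy in the Change Interview. The row names no instrument, dependent variable or factor. No social-desirability scale appears in Outcome Measures, the Table of Outcomes or the Schedule of Procedures. The note under the schedule points elsewhere for detail ("see Timetable of Measures for outline of when individual measures are administered"). Neither that timetable nor the contents of Questionnaire Pack 1.1 are in the text available for this review. The analysis line of the Study Summary reads "Reliable Change Index; adjudication panel; Framework Analysis; correlations; visual analysis" and does not mention ANCOVA.

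**Design.** Under Sampling and size of sample: "The study will recruit up to four participants". Under Randomisation and Blinding: "Participants in this study will not be randomised or blinded to any aspects of the study". No comparison group is described.

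**HAT.** Table 1, row 2 (process-outcome mapping) has a single method: "Correlations between within therapy measures (HAT), and quantitative outcome measures", by Pearson, or by Spearman if normality fails. Row 5 (event-shift sequences) sets the HAT against the Personal Questionnaire (PQ, called SPQ in the tables) by correlation and by visual analysis. The Session measures list describes the HAT as qualitative, filled in by the therapist together with the client after each session. No numeric item or coding rule is stated.

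**The concern.** An ANCOVA needs a covariate that varies over the units analysed, and usually a factor whose levels are compared. Here the covariate is not listed, the design has no groups, and each case is to be judged on its own record. A correlation needs two numeric or ordinal series, and one of the two is described only as qualitative.

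Two things are at stake. First, the ANCOVA is meant to help the sceptic brief show whether reported change reflects a wish to please. If it cannot be estimated, that line of argument rests on the interview alone while appearing to have a quantitative test behind it. Second, rows 2 and 5 are two of the five areas of affirmative evidence, and Study Design requires evidence in two areas before a case goes to adjudication. With no HAT coding set in advance, the coding would be chosen later, by default by the student researcher/therapist, who both completes the HAT with the client and performs the analyses.

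**Working it through.** **1. The plan's own sample size.** Sampling and size of sample justifies three cases and cites dropout of about 25%. 3 / (1 − 0.25) = 4, so the planned maximum of four is reproduced. The checks below use four and three clients.

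**2. ANCOVA within one case.** The Table of Outcomes and the Schedule of Procedures give 7 occasions for the main scales: four baselines (the fourth is also the pre-therapy point), mid, post and follow-up. Take a model with an intercept, a phase term (four occasions up to the start of therapy, three after) and a social-desirability score taken once. The score is the same number on all 7 rows, so it is a multiple of the intercept. The design matrix has 3 columns and rank 2. The effect of the score cannot be estimated.

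**3. ANCOVA pooled over clients.** With client indicators, phase and a once-per-client score:
- four clients: 6 columns, rank 5;
- three clients: 5 columns, rank 4.

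The score is a linear combination of the client indicators, so it is aliased with client. Leaving the indicators out would only treat repeated measurements of the same person as independent replicates.

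**4. ANCOVA across clients, one row per client.** Residual df = clients − parameters.

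| Model | Parameters | Four clients | Three clients |
|---|---|---|---|
| Change on score | 2 | 2 df | 1 df |
| Post on pre plus score | 3 | 1 df | 0 df |

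The 97.5% point of t is 4.303 at 2 df and 12.706 at 1 df. A 95% interval is therefore about ±4.3 or ±12.7 standard errors, and undefined at 0 df.

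**5. The exception.** If social desirability were scored on several occasions, a within-client model could be fitted. The available text gives no such schedule.

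**6. HAT correlations.** As described, the HAT supplies no stated score, so neither coefficient can be computed from what the plan specifies. Suppose it were coded once per session, with 12 sessions attended (the plan offers up to 12):
- OPQOL-brief, HADS and CompACT-8 fall on a therapy session at the pre, mid and post points only: session 1 (ideally the day of the fourth baseline), usually session 6, and session 12. That is 3 same-session pairs per case. The smallest exact two-sided Spearman p-value is 2 / 3! = 0.333. Pearson's |r| would have to reach 0.997 at a two-sided 5% level, which is my assumption because the plan states no level.
- The Outcome Rating Scale (ORS) and the PQ are weekly, giving up to 12 pairs, where the corresponding |r| is 0.576.

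Row 2 lists only correlation, so it has no usable method until a score is defined. Row 5 keeps its visual analysis.

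**The case against.** The strongest reply is that these are supporting inputs to an interpretive, panel-adjudicated case series with no stated significance level. The two-area rule only admits a case to the panel; it does not establish efficacy, and a sceptic brief answers every affirmative one. Table 2 row 3 still has the Change Interview, held by someone the participant has not dealt with before. Row 5 still has visual analysis. Row 2 may be meant to include the weekly ORS and PQ, which are also outcome measures. All of this stands, and it limits the weight of the point. It does not make the ANCOVA estimable from a once-per-client score or supply a HAT score. The missing ANCOVA in the one-line summary is weak evidence and carries no weight here.

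A reader might infer more than the documents support, in four ways:
- *That social desirability will not be measured, or that the HAT form cannot yield a number.* The timetable, the questionnaire pack and the HAT form are not in the available text. The supported statements are that no instrument is listed and no score or coding rule is stated.
- *That Table 1 row 3 fails too, because its method cell gives no lag.* Its adherence, ORS and PQ data are all collected at session level and can be correlated, and its description cell already speaks of change from week to week. Outcome Measures defines the ORS as a weekly rating, so the mere fact that it is completed after a session does not fix a correct lag.
- *That dropout to three would be a shortfall.* Three is the number of cases the plan justifies, and under Withdrawal, "A replacement participant will be recruited, dependent of timeframe and ability to deliver therapy".
- *That the efficacy conclusion is undermined.* It does not rest on these cells.

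**Conclusion.** The point holds for three table cells. Table 2 row 3 names an analysis that the described design cannot deliver: not estimable within a case, aliased with client when pooled, and left with 0 to 2 residual df across clients. This rests on the score being taken once per client; repeated scoring would change it. Table 1 rows 2 and 5 correlate a form described as qualitative, with no score or coding rule stated. The gap is greater in row 2, where correlation is the only method and where a coded HAT would give about three same-session pairs per case with the primary outcome scale, assuming 12 sessions.

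This lies between a minor point and one that should be fixed, since it concerns supporting evidence only. The OPQOL-brief outcome, the Reliable Change Index calculations, the Change Interview and the adjudication stand as planned.

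**What to change.** - **Table 2, row 3.** Drop the ANCOVA. Judge relational artefacts descriptively for each case from the Change Interview, keeping the independent interviewer. If the Timetable of Measures does schedule a social-desirability score, name the instrument and report the score descriptively per case.
- **Table 1, row 2.** Replace the correlation with a per-case narrative that maps the helpful processes reported on the HAT to the content of post-therapy change, drawn from the Change Interview and from the outcome measures with their Reliable Change Index results.
- **Table 1, row 5.** Rely on a visual event-shift display: HAT events at session t against the change in PQ from before session t to before session t+1.
- **Both HAT rows.** Keep them as separate evidence areas, so that one display does not count twice towards the two-area threshold. Fix any HAT coding rule before therapy starts, because the therapist sees the PQ scores as sessions go on.

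The cost is rewording three cells and adding a sentence on coding. No new data, staff or software are needed. The downside is slightly more descriptive work and evidence that looks less quantitative.
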